### 7.7 Subject monitoring during surgery

All subjects will be monitored continuously according to local routines, including pulse oximetry (SaO2) and the arterial radialis pressure in arm of the non-surgical side, expired CO2, pressure/volume spirometry, a peripheral intravenous access and electrocardiography (ECG).

### 7.8 Extubation

Prior extubation of the subject, the tracheal and endobronchial cuffs is deflated completely by inserting a syringe into valve housing and removing the gas mixture, until a definite vacuum is noted in the syringe and the pilot balloon collapsed. The extubation is performed slowly.

- *Information about the extubation must be recorded in the CRF (smooth extubation, did the subject cough, did the subject complain of throat pain).*
- *General information (adverse events, complications, deviations from protocol) about the procedure must be recorded in the CRF after extubation is completed.*

For the test group, the single use adaptor cable is disconnected from the aView monitor after extubation, and the aView monitor is turned off by pressing the power button for at least two seconds. The DLT (VivaSight-DL or Shiley) and single-use accessories are discarded after use.

### 7.9 Awakening of subject and follow up

Immediately after the surgery, the physician is asked to complete a questionnaire regarding the procedure just performed (Appendix VI).

All subjects are woken up immediately after surgery. Within forty-eight hours after the surgery, the subject will be contacted (in the hospital room or over the phone) by a research assistant who will ask questions regarding the subject's health-related life quality and potential side effects from the intubation (Appendix V). It will be the same research assistant who contacts all subjects in order to ensure identical data collection across subjects.

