## 5. DESIGN OF INVESTIGATION

### 5.1 Design of investigation

A randomized, controlled single-centre investigation comparing the VivaSight-DL and the conventional DLT at a teaching hospital. A pilot study including up to 10 subjects will be performed prior to the investigation is initiated (see section 7.1). The investigation will include a total of 50 adult subjects (25 subjects in each group) admitted to department V at OÜH with established indication of single lung ventilation.

The objective of the investigation is to compare the number of times the tube position needs to be verified with a scope and relevant costs between VivaSight-DL and conventional DLT in a cost-effectiveness analysis. Furthermore, procedure time, intubation attempts and repositioning will be assessed (see section 4. End Points).

The study will start to recruit subjects within four weeks after Ethical Committees approval and nine months ahead or until 50 subjects have been recruited. If the number of subjects cannot be included in time, the sponsor and Principal Investigator will decide if the study should be closed.

Each subject enrolled in the investigation can only participate in the investigation once. The study duration for each subject is counting from the indication of the need of a single lung ventilation procedure until the subject has completed the questionnaire. Only one test device should be used per subjects (VivaSight-DL or conventional DLT).

Only subjects who can be clinically evaluated as eligible for a single lung ventilation procedure i.e. complies with the listed inclusion and exclusion criteria may be included in the investigation. If subjects or their legal representatives do not consent to the investigation or if the subject is not assigned a novice physician to perform the procedure, the procedure will be performed regardless – however off this investigation. A Case Report Form (CRF, appendix III) must be filled in for each subject that is assigned a novice physician to perform the intubation and has signed the Informed Consent (appendix II), and therefore is included in the investigation. After the surgery the subjects will be asked to answer a questionnaire regarding health-related life quality and side effects from the procedure (appendix IV). If the subject cannot give feedback, the reason is stated in the questionnaire.

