## Tertiary end-points

- Qualitative measures (questions to the patient)
  - Any side effects from the surgery: Data will be summarized using frequency tables and examined via regression model as suitable.
  - Daily function level prior surgeryPostoperative scores will be summarized in a frequency table and examined via regression model as suitable.
- Qualitative measures (questions to the person who intubated)
  - Ease of tube placement (on a scale from 1=very easy to 5=very difficult)
  - How would you rate the overall perception of quality and functionality of the tube (DLT or VivaSight)? (Very poor, poor, acceptable, good, very good)
  - Would you prefer to use this method for single lung ventilation in the future? (yes/no)

A Chi-sqaure test will be applied to examine whether qualitative measures are significantly different for procedures using VivaSight-DLT compared to a conventional DLT.

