## APPENDIX VI: QUESTIONNAIRE FOR SUBJECTS

### Spørgeskema omhandlende helbredsrelateret livskvalitet og bivirkninger efter operation i hjerte-lunge området

I forbindelse med at De har deltaget i et forskningsstudie og har fået foretaget en operation med behov sikring af dine luftvejene på Odense universitetshospital, vil vi bede Dem besvare nedenstående spørgeskema omhandlende din generelle helbredsrelaterede livskvalitet samt eventuelle bivirkninger efter din operation.

Forsøgsperson nummer: \_\_\_\_\_

Dato for udfyldelse: \_\_\_\_\_

Tidspunkt for udfyldelse: \_\_\_\_\_

Spørgsmål omhandlende helbredsrelaterede livskvalitet						Kommentarer
Hvordan vil De vurdere Deres overordnet livskvalitet indenfor de sidste 4 uger?	 Dårlig	 Mindre god	 God	 Meget god	 Fremragende	
I hvor høj grad har De haft smerter indenfor de sidste 4 uger?	 Slet ikke	 I mindre grad	 I nogen grad	 I høj grad	 I meget høj grad	
I hvor høj grad har Deres smerter påvirket Deres hverdag?	 Slet ikke	 I mindre grad	 I nogen grad	 I høj grad	 I meget høj grad	
I hvor høj grad har De følt dem ængstelig eller deprimeret indenfor de sidste 4 uger?	 Slet ikke	 I mindre grad	 I nogen grad	 I høj grad	 I meget høj grad	
Hvordan vil De vurdere Deres helbred alt i alt?	 Dårligt	 Mindre godt	 Godt	 Meget godt	 Fremragende	
Spørgsmål omhandlende eventuelle bivirkninger efter operationen						Kommentarer
Hvor mange timer er der gået siden Deres operation?	 0-4	 5-9	 10-14	 15-19	 Over 20	
Har De tidligere fået foretaget en lignende operation?	 Ja	 Nej				
Har De oplevet hoste efter Deres operation?	 Ja	 Nej				

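### Side-effect questionnaire (tertiary endpoint): one contact at any time up to 48 hours after surgery gives subjects unequal exposure, and early contacts miss later symptoms

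*Combined protocol and SAP*

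**What the plan says.** Section 7.9 of the protocol fixes the follow-up contact: "Within forty-eight hours after the surgery, the subject will be contacted (in the hospital room or over the phone) by a research assistant". No minimum or target time is given. The same section standardises the interviewer: "It will be the same research assistant who contacts all subjects in order to ensure identical data collection across subjects". Under 5.1 the subject's participation runs "until the subject has completed the questionnaire", so no later contact follows.

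The subject questionnaire (Appendix VI; 7.9 cites it as Appendix V) asks how many hours have passed: "Hvor mange timer er der gået siden Deres operation". The boxes are 0-4, 5-9, 10-14, 15-19 and over 20. The form also carries the date and the clock time of completion ("Tidspunkt for udfyldelse"). The cough item reads "Har De oplevet hoste efter Deres operation", that is, whether cough has occurred after the operation. Hoarseness and throat pain are asked in the same way, each with a severity grade if the answer is yes.

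The analysis is in 18.3.3 under the tertiary endpoints: "Any side effects from the surgery: Data will be summarized using frequency tables and examined via regression model as suitable". A chi-square test between the tubes is then applied to the qualitative measures. Elapsed time is not named in any of these analyses.

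**The concern.** The symptom items accumulate. A subject asked at 4 hours can report only what happened in 4 hours, while a subject asked at 48 hours reports on twelve times as long. Both answers enter the same frequency table and the same test. The plan keeps one interviewer so that data collection is identical across subjects, but the same question asked at 4 and at 48 hours does not measure the same thing.

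At stake is the structured patient-reported comparison of side effects. Under-counting lowers the reported rates. If it is similar in both arms, it also shrinks the absolute difference and so makes a finding of no difference easier to reach.

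**Working it through.** **The plan's own figures.** The plan states no rate, power or sample size for side effects. Its only computed design figure is the sample size for the primary outcome (18.1): (0.23622 + 0.01087) × (1.96 + 1.28)² / (0.37234 − 0.01087)² = 0.24709 × 10.4976 / 0.13066 = 19.85 per arm, so N = 40, and 40 / 0.80 = 50. This reproduces. It is not an input here and nothing below changes it.

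**Exposure allowed by the text.** 7.9 gives the upper limit of 48 h. The first box of the hours item shows that contacts within 0-4 h are foreseen. The last box covers 48 − 20 = 28 of the 48 permitted hours (28/48 = 58%).

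**Where else symptoms are recorded.** Cough and throat pain are noted in the CRF at extubation (7.8 and the CRF); hoarseness is not. The CRF also has yes/no fields for adverse events and airway complications, and 13.2 requires all adverse events to be recorded and reported. No other scheduled postoperative contact with the subject is described.

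**Illustration of the under-count.** The documents give no onset times, so these are assumptions shown as a range. Let *h* be the onset half-time, k = ln 2 / h, and F(t) the share of subjects who would say yes at 48 h and who already say yes at *t*:

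F(t) = (1 − e^(−kt)) / (1 − e^(−48k))

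Example, h = 12: F(4) = (1 − 0.794) / (1 − 0.0625) = 0.22; F(24) = (1 − 0.25) / 0.9375 = 0.80.

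For contacts spread evenly from *a* to *b* hours, mean capture = [1 − (e^(−ka) − e^(−kb)) / (k(b − a))] / (1 − e^(−48k)). Example, h = 12, 24 to 48 h: [1 − (0.25 − 0.0625) / 1.386] / 0.9375 = 0.92.

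| Assumed half-time | Capture at 4 h | Capture at 24 h | Mean, 0-48 h | Mean, 24-48 h |
|---|---|---|---|---|
| 3 h | 60% | 100% | 91% | 100% |
| 6 h | 37% | 94% | 82% | 98% |
| 12 h | 22% | 80% | 71% | 92% |
| 24 h | 15% | 67% | 61% | 85% |

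An assumed 48-hour incidence of 40% would therefore read as 24% down to 6% at 4 h (0.40 × capture), and as 40% down to 27% at 24 h. If symptoms are nearly all present on waking, F is close to 1 from the start and the loss is small.

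**Effect on the comparison.** If both arms have the same mean capture *c*, a true difference p₁ − p₂ is observed as c(p₁ − p₂). If the true rate is *p* in both arms but capture differs, the spurious difference is p(c₁ − c₂). With the same onset pattern in both arms, this is zero when contact times are distributed alike.

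**The case against.** The strongest reply is that the data needed for a repair are already collected. The coarse last box might lead a reader to infer that timing cannot be recovered. The documents do not support that: the form records the completion date and clock time, the CRF records the date of surgery and knife end, and the planned regression leaves room for a covariate. This stands, with two limits. The plan does not specify such a covariate, and no adjustment recovers a symptom that begins after an early contact.

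A reader might also infer that tolerability is otherwise unrecorded after surgery. That is too strong, given the extubation items, the CRF fields and the adverse-event reporting duty. But the extubation items describe one early moment and omit hoarseness.

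A third tempting inference is bias between the arms. Randomisation balances contact time in expectation. The documents do not describe a blinded interviewer, but nothing in them suggests that one arm would be contacted earlier. Chance imbalance with 25 per arm is possible; systematic imbalance is not shown.

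Finally, one might attach a definite loss of power. That would need symptom rates, onset times and a distribution of contact times, none of which the documents give. It would also have to allow for the Bonferroni correction in 18.3.4, whose family is not defined. The trial is sized on bronchoscope use, so this comparison is unpowered even with ideal timing.

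**Conclusion.** The point holds as a minor one. Followed as written, the plan gives subjects unequal exposure, under-counts symptoms that start after an early contact, and analyses the answers without regard to elapsed time. The direction is certain for symptoms of later onset. The size is not known: the capture figures rest on an assumed exponential onset with half-times of 3 to 24 hours, and the loss could be negligible if symptoms are mostly present on waking.

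The consequence is confined to a tertiary endpoint. The aim is health-economic, the hypothesis concerns bronchoscope use, and patient-reported side effects are not among the effect measures in 18.7. No primary or secondary result is affected.

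**What to change.** 1. In 7.9, add a lower limit inside the existing window, for example contact between 24 and 48 hours after surgery, by phone if the subject has been discharged (7.9 already allows the phone).
2. Derive exact elapsed hours for each subject from the questionnaire's completion date and time and the CRF's date of surgery and knife end. The CRF has no extubation time, so knife end is a reasonable proxy for the start.
3. In 18.3.3, state that elapsed hours will be reported by arm and included as a covariate in the regression already planned for side effects.

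This costs a phrase in 7.9, one derived variable and a sentence in 18.3.3, with no extra visit and no change in sample size. The downsides are less scheduling freedom for the single research assistant and about one day's recall of early symptoms. Exposure can still differ up to two-fold (48/24), which is why the covariate is worth keeping. The choice of 24 hours is a judgement. The lower limit should be settled before enrolment, because contact time cannot be standardised afterwards.

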# Clinical Investigation Plan (CIP)

Study Name: VivaSight-DL study (CIS-009)  
Ethical committee number: S-20180081

CLI-000427

Rev. 02

## 7.10 Collection of cost data

To enable an exact cost-model of single-lung ventilation, it is necessary to fully understand all processes related to the procedure. A research assistant will map all processes related to the procedure at the investigational site. Based on this, the research assistance collects all costs related to single-lung ventilation.

Resources and personnel time used for the individual processes will be tracked on a worksheet based on the initial mapping of the processes related to single-lung ventilation. This includes but is not excluded to personnel cost, procedure times, utilities, single-use equipment and capital equipment used during single-lung ventilation. Furthermore, all resources and times related to bronchoscopes will be collected via following at least 5 bronchoscopes from storage/drying cabinets through procedure, cleaning, reprocessing and back to storage/drying cabinets.

The following cost data will be collected via the investigational sites own records: Capital cost, repair costs, maintenance cost, cost of service agreements, cleaning verification costs, audit costs, personnel costs, cost of single-use equipment, administrative costs, cost of utilities and detergents. Note that if additional related costs are detected during the study they will be included in the cost-model.

## 8. MATERIALS

### 8.1 Test device

#### 8.1.1 General information and device description

VivaSight-DL is manufactured by ETVView Ltd ([name]), and is a sterile single-use, left sided, double-lumen cuffed PVC endobronchial tube with an embedded video imaging device and light source at the distal end of the tracheal lumen, and an integrated single use video/power cable (adapter cable) with connector.

VivaSight-DL displays images of the airway onto the Ambu® aView™ monitor (Ambu A/S, [name]) for as long as the device remains in place during intubation. VivaSight-DL has two color-coded low-pressure cuffs with corresponding pilot balloons. Additionally, for cleaning the imaging lens, the VivaSight-DL has an injection port leading to two lumens along the tube's wall, which opens at the distal end of the imaging lens. The VivaSight-DL System is intended to isolate the left or right lung of a patient for intensive care or surgery, one lung ventilation or one lung anesthesia.

The VivaSight-DL is CE-marked (CE 0483) and thereby approved for sale in Europe. It comes in four sizes as specified in the table below.

# Clinical Investigation Plan (CIP)

Study Name: VivaSight-DL study (CIS-009)  
Ethical committee number: S-20180081

CLI-000427

Rev. 02

	35 Fr Left	37 Fr Left	39 Fr Left	41 Fr Left
Size	35 Fr	37 Fr	39 Fr	41 Fr
ID (mm)	4.0	4.2	4.8	5.0
OD (mm)	10.5	11.5	11.5	12.0
Length (+2/omm)	330	330	330	330

All VivaSight materials that are in contact with the patient, have been tested for biocompatibility with reference to ISO 10993 (10), current version.

## 8.1.2 Precaution and handling

The system must not be used if, in the opinion of a qualified physician, such an application would endanger the patient or if the system as such or the method is contraindicated. Such cases will not be considered as part of the study.

The Ambo® VivaSight system must be used by doctors and nurses trained in single lung ventilation and handled according to the Instructions for use (IFU).

## 8.2 Comparative device

### 8.2.1 General information and device description

The Shiley endobronchial tube is manufactured by Covidien Ilc. ([name]) and is a sterile single-use endobronchial tube with a left or right Bronch-Cath™ option, depending on the lung that needs to be ventilated. The tube features a low pressure tracheal and bronchial cuff to minimize risk of mucosal damage. The specially designed bronchial cuff assists with location of the distal tip when verification is confirmed by a fiber-optic bronchoscope. There is a slight curve at the distal tip to assist with placement. There is also an x-ray opaque carinal hook for confirming placement.

The Shiley endobronchial tube is CE marked (CE 0123) and thereby approved for sale in Europe. The sizes that will be used in this study is specified in the table below.

	35 Fr Left	37 Fr Left	39 Fr Left	41 Fr Left
Size	35 Fr	37 Fr	39 Fr	41 Fr
ID (mm)	4.8	5.1	5.3	5.4
OD (mm)	11.7	12.3	13	13.7

# Clinical Investigation Plan (CIP)

Study Name: VivaSight-DL study (CIS-009)  
Ethical committee number: S-20180081

CLI-000427

Rev. 02

## 8.3 Supplementary materials and equipment

In addition to the test device and the comparative device, the following equipment will be available for use during the procedure:

- Direct laryngoscope
- Suction catheter
- Pentax FI-10BS (Pentax, USA)
- Olympus LF-V (Olympus, Japan)

## 8.4 Investigator's Brochure

As the devices are approved for sale (CE-marked), an Investigator's Brochure is not required. The IFU will be available in the packaging of the devices.

## 8.5 Device Accountability and Traceability.

The sites included in the study will make their conventional bronchoscopes available as comparator for this investigation.

The site will free of charge receive 40 Ambu® VivaSight-DL devices. For this study two Ambu® aView™ monitors will be provided as well. Any devices remaining after the end of the study will be accounted for and shall be returned to Ambu®.

There are no requirements regarding device accountability for CE marked devices. However, for logistical reasons the Sponsor will account for all devices delivered to and returned from the Investigators in a Device Accountability Form kept at Sponsor's address.

# 9. MONITORING

During the period of the study, a representative of the Sponsor will act as monitor of the study. The Investigator may contact Sponsor representatives, as listed on page 3, at any time.

## 9.1 Monitoring Visits

During the period of the investigation a representative of the sponsor will perform an initiation visit, monitor visits and close out visits on site or per distance.

- Initiation Visit: This meeting will be held before the study is initiated, and the aim of this meeting is to train the investigators and research assistants on the investigation procedure, perform a page-by-page revision of the protocol with emphasis on reporting of deviations, adverse events and how to complete the CRF. Moreover, contract signature and approvals from authorities will be verified, and monitoring arrangements will be discussed. It is required that *all* investigators participating are present in this meeting.
- Routine Visit: The aim of these monitoring visits is to corroborate the study progress and perform source data verification. CRF will be monitored for completeness and correctness of the data. It is required that at least one investigator is available during monitoring visits. A monitor visit will be done at each of the investigation site after 3-6 subjects completing the study.
- Close-out visit: The aim of this meeting is to close financial aspects, check that all essential documents are complete and up to date, all outstanding queries are resolved, current state of all adverse events is documented, arrangement for achieving all study documentation, device accountability, collection of the original CFR, and notification of the corresponding authorities. This meeting will be conducted after the last subject has been completed or no later than three months after finishing the data collection.

The monitor is responsible for planning the monitoring visit

# Clinical Investigation Plan (CIP)

Study Name: VivaSight-DL study (CIS-009)  
Ethical committee number: S-20180081

CLI-000427

Rev. 02

## 9.2 Source Data Verification

The Case Report Form, Informed consent, and Patient Registration List will be verified against the subject's medical record for the following parameters:

- Subject identification
- Reason for hospitalization
- Inclusion/exclusion criteria
- Adverse events
- Completion/Drop out
- Subject's participation in the investigation

Data verification will be done for 20% of the subjects participating in the study. If any inconsistencies is found between study data and the medical record, data verification will be performed for all subjects.

## 10. AUDIT

Audit of the clinical investigation may be conducted by the Sponsor or third parties designated by the sponsor to evaluate compliance with the CIP, written procedures and International Standards (6). These audits may cover all involved parties, systems and facilities and are independent from routine monitoring. The aims of the audit are:

- to assess the effectiveness of the monitoring,
- whenever there are repetitive deviations from the CIP,
- to prepare the investigation for a regulatory inspection,
- when requested by a regulatory authority, etc.

Audits may be performed during the investigation. All parties will be informed in advance of the date and objective of the audit.

## 11. CLINICAL INVESTIGATION PLAN

The CIP was made according to the Council Directive 93/42 EEC of 14 June 1993 and amendment 2007/47/EC (5), the guidelines set out in ISO 14155 (6), ISO 14971 (7), and the Helsinki Declaration (8).

An example of the Case Report Form is enclosed in the CIP together with the Patient Information and Informed Consent. The Case Report Form is in English and should be filled in English when possible. Missing data not recorded on the day of the procedure should be filled in later accompanied by date and signature. Data that are evaluated as incorrect by Investigator should be crossed over with ink allowing the "old data" to be seen (example). The Investigator shall then write the new and correct data and then sign and date.

Any discrepancies compared to the procedures described in this CIP shall be documented and reported to the Sponsor or monitoring person.

The Sponsor and the Investigator must sign the CIP before the investigation can start at the centre.

